4.1. Inclusion Criteria

Each potential subject must satisfy all of the following criteria to be enrolled in the study:

1. Criterion modified per Amendment 2:
 - 1.1. Criterion modified per Amendment 3:
 - 1.2. Men or women ≥ 18 years of age (or the legal age of consent in the jurisdiction in which the study is taking place), defined at the time of randomization.
2. Hospitalized (or in emergency room prior to hospitalization) at the time of randomization and unlikely to be discharged for the first 24 hours after randomization.
3. Criterion modified per Amendment 2:
 - 3.1. Diagnosed with RSV infection based on PCR-based assay with or without co-infection with another respiratory pathogen (eg, influenza, human metapneumovirus, or bacteria).

NOTE: in cases where commercial PCR-based assays are not available at the site, the sponsor should be consulted for agreement on the assay to be used.

4. Criterion modified per Amendment 2:
 - 4.1. Has an acute respiratory illness with signs and symptoms consistent with a viral infection (eg, fever, cough, nasal congestion, runny nose, sore throat, myalgia, lethargy, shortness of breath, or wheezing) with onset ≤ 5 days from the anticipated time of randomization.

NOTE: The viral infection may present in any way as long as the underlying precipitant of the illness is considered by the investigator to be due to RSV infection. Examples of such an illness include:

- An upper or lower viral respiratory tract infection (eg, “flu-like illness”)
- Pneumonia
- Respiratory distress
- Asthma exacerbation
- Chronic obstructive pulmonary disease (COPD) exacerbation

5. Criterion modified per Amendment 2:
 - 5.1. With the exception of the RSV disease, medically stable on the basis of medical history, physical examination, vital signs, and 12-lead ECG performed at screening. If there are abnormalities, they must be consistent with the underlying illness in the study population and/or the RSV infection. This determination must be recorded in the subject’s source documents and initialed by the investigator.

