8. PRESTUDY AND CONCOMITANT THERAPY

Prestudy therapies administered up to 7 days before first dose of study drug must be recorded at screening.

All subjects will receive supportive care according to local institution standard. While treatment guidelines and standards vary based on local practice and should be considered in the management of subjects, within the parameters of this study, it is recommended that supplemental oxygen can be administered or withdrawn, as appropriate to maintain an SpO₂ ≥93% (for subjects whose baseline SpO₂ is ≥93% when clinically stable).

Concomitant therapies must be recorded throughout the study beginning with start of the first dose of study drug to the Day 28 visit (±2 days). During hospitalization, concomitant medication will be recorded by the site staff in the eCRF. Upon discharge, subjects will be required to document use of concomitant medication in the electronic device in a medication log, which will serve as basis for recording the concomitant medication in the eCRF by the site staff.

Concomitant therapies should also be recorded beyond Day 28 in the subject's medical notes and reported by SAE forms (if applicable) only in conjunction with SAEs that meet the criteria outlined in Section 12.3.2.

All therapies (prescription or over-the-counter medications, including vaccines, vitamins, herbal supplements, home oxygen therapy; non-pharmacologic therapies such as electrical stimulation, acupuncture, special diets, exercise regimens) different from the study drug must be recorded in the eCRF. Recorded information will include a description of the type of the drug/therapy, treatment phase, the dose regimen, route of administration, and its indication. Modification of an effective preexisting chronic therapy should not be made for the explicit purpose of entering a subject into the study, however if a subject has received acute doses of a prohibited drug, switching to an alternative drug chosen at the discretion of the investigator is allowed.

Concomitant medications are permitted as indicated for the management of study subjects with the exception of the medications noted here. The following medications are not permitted during the study and for the time period prior to randomization as noted:

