 - Supplemental oxygen above pre-RSV disease level (regardless of method used) from study treatment initiation to Day 7.
 - Oxygen delivered by noninvasive ventilator support (eg, continuous positive airway pressure) and/or invasive ventilator support (eg, endotracheal-mechanical ventilation or mechanical ventilation via tracheostomy).
 - Subjects (proportion) who started antibiotic use after the first dose of the study drug.
- Disease status and presence of complications with onset after treatment initiation:
 - Bacterial superinfections reported as AEs (eg, pneumonia, acute otitis media, sinusitis, bronchitis, bacteremia).
 - Exacerbations of underlying pulmonary disease (eg, asthma, chronic obstructive pulmonary disease).
 - Cardiovascular and cerebrovascular events (eg, myocardial infarction, congestive heart failure exacerbation, arrhythmia, stroke).
 - Respiratory failure
 - *Clostridium difficile* associated diarrhea
 - Other

- Duration and severity of signs and symptoms of RSV infection as assessed by the respiratory infection patient-reported outcome (RI-PRO) questionnaire and additional questions about health and functioning completed by the subject in the eCOA.
- HRQoL assessed by the EuroQoL 5 Dimension visual analogue scale (EQ-5D VAS) completed by the subject in the eCOA.
- Hospital readmission for respiratory reasons up to the Day 28 follow-up visit.
- RSV RNA viral load (AUC) as measured by qRT-PCR of endotracheal samples in intubated subjects.
- Lung function measured by the DLCO and spirometry test.
- RSV infectious viral load as measured using a quantitative viral culture (plaque assay).

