4.2.4. Secondary Efficacy Endpoints

4.2.4.1. Definition

Formulae to be used for derived variables, including data conversions, are provided in [Table 1](#). In the derivation of durations described below, no imputation of the start and/or end date/time will be performed.

Table 1. Calculations and Conversion Formulae

Measurement	Formula
Length of hospital stay (hours) [Time-to event]	(Date and time of event or censoring - date and time of first dose of study drug)/3600, rounded to one decimal
Time to readiness for discharge (hours) [Time-to-event]	Subjects who complete or withdraw from the study prior to the event will be censored at the date of completion or withdrawal. If the time is not available they will be censored at 12:00. In case of death prior to an event the time of death will be taken as censoring time (or 12:00 if not available).
Length of hospital stay since hospital admission (hours) [Time-to event]	(Date and time of event or censoring - date and time of hospital admission)/3600, rounded to one decimal
Time to readiness for discharge since hospital admission (hours) [Time-to-event]	Subjects who complete or withdraw from the study prior to the event will be censored at the date of completion or withdrawal. If the time is not available they will be censored at 12:00. In case of death prior to an event the time of death will be taken as censoring time (or 12:00 if not available).
ICU duration of stay (hours) [Duration]	sum of [(end date and time of event - start date and time of event)/3600], rounded to one decimal
Duration of supplemental oxygen (hours) [Duration] (3 separate parameters: supplemental oxygen, invasive ventilator, non-invasive ventilator)	If the end date is missing, the end date is considered to be after study completion or withdrawal. If the initial start time is prior to the first dose of study drug, the duration prior to the first dose of study drug will be deducted from the overall duration.
Need for feeding, hydration by IV catheter/enteral tube (hours) [Duration] (2 separate parameters)	If the end date and time is after the study completion/discontinuation, the duration after the date and time of study completion/discontinuation will be deducted from the overall duration. If the time is not available it will be put at 12:00.
Time to end of Oxygen supplementation (hours)	(Date and time of event or censoring - date and time of first dose of

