
[Time-to-event] (3 separate parameters: overall, invasive, non-invasive)
 
Time to end of supplementation feeding, hydration (hours) [Time-to-event] (2 separate parameters)
	
study drug)/3600, rounded to one decimal
 
The event is defined as the last end date and time of the measured parameter (supplemental oxygen, invasive oxygen, non-invasive oxygen, feeding or hydration). If this date is missing, the end date is considered to be after study completion or withdrawal.
 
Subjects who complete or withdraw from the study prior to the last end date and time of the measured parameter will be censored at the date of completion or withdrawal. If the time is not available they will be censored at 12:00. In case of death prior to the last end date and time of the measured parameter, the time of death will be taken as censoring time (or 12:00 if not available).
 
If no oxygen supplementation, supplemental feeding or hydration was necessary post baseline, the value will be set to 0.

Time point of SpO2 \geq 93% on room air
	
The first time point with SpO2 \geq 93%, where no supplemental oxygen supplementation is given at or after this time point and where no value $<$ 93% are measured after this time point.

Time to SpO2 \geq 93% (hours) on room air [Time-to-event]
	
minimum[date and time of time point with SpO2 \geq 93% on room air, date and time of last SpO2 measurement] - date and time of first dose of study drug)/3600[†], rounded to one decimal
 
Subjects with SpO2$<$93% on room air or who are still on oxygen supplementation at the last SpO2 assessment will be censored at the date and time of the last SpO2 assessment.
 
This parameter will only be calculated for subjects who were not on supplemental oxygen prior to current hospitalization

Time point of return to pre-RSV disease level (hours) for HR, RR, SpO2 (3 separate parameters)
	
The first time point where it is indicated by the investigator that the observed value is normal for the subject, and for none of the time points after this point in time the values are indicated to be abnormal for the subject (separate for HR, RR or SpO2).

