The need and duration of supplemental oxygen will be analyzed by splitting the ITT-i population into two partitions:

- 1) Those patients who require supplemental oxygen before treatment initialization
- 2) Those patients who did not require supplemental oxygen before treatment initialization

Both partitions will be analyzed separately, answering two different questions:

- 1) For those patients who require supplemental oxygen before treatment initiation: Is there a treatment difference in the time to no longer requiring supplemental oxygen? This analysis will be performed primarily with a Kaplan-Meier analysis and a stratified Gehan test.
- 2) For those patients who did not require supplemental oxygen before treatment initialization: Is there a treatment difference in preventing the use of supplemental oxygen? This partition will be analyzed using a stratified (exact) logistic regression model as specified above.

While we cannot integrate these results they are conceptually linked. We will combine the p-values for both independent tests for the comparison of each active group versus placebo using the method of Liptak^[3].

In addition to the analysis described above, the time to no longer requiring supplemental O₂ will be analyzed on the total group of subjects where subjects who do not require supplemental oxygen during the study are considered to have their event at time 0. As before, this will be analyzed in an exploratory sense using Kaplan-Meier analysis and with a stratified Gehan test to test for treatment differences.

This analysis will be repeated by method of administration (invasive, non-invasive).

The analysis for the need and duration of supplemental feeding and supplemental hydration will be done in similar fashion as for supplemental oxygen use described above.

Time to SpO₂ ≥ 93% (hours) on room air

Time to SpO₂ ≥ 93% (hours) on room air will be summarized and listed for subjects who were not on supplemental oxygen prior to current hospitalization.

Among subjects who were not on supplemental oxygen prior to current hospitalization, the time to SpO₂ ≥ 93% (hours) on room air, will be summarized and analyzed in an exploratory sense using Kaplan-Meier analysis.

The time from first dose to SpO₂ ≥ 93% (hours) on room air will also be analyzed using AFT methodology.

Time to return to pre-RSV disease level (hours) for RR, SpO₂; body temperature

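### End and duration of supplemental oxygen are counted with no reference to the pre-RSV level, which dilutes the planned comparison if long-term home-oxygen users are enrolled

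*SAP*

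**What the plan says.** SAP 4.2.4.1, Table 1, has two relevant rows.

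- **Time to end of oxygen supplementation.** "The event is defined as the last end date and time of the measured parameter". For an open record: "If this date is missing, the end date is considered to be after study completion or withdrawal". Then: "Subjects who complete or withdraw from the study prior to the last end date and time of the measured parameter will be censored", with censoring at completion or withdrawal.
- **Duration of supplemental oxygen.** Recorded periods are summed. Only time before first dose and time after study end is removed. "If the end date is missing, the end date is considered to be after study completion or withdrawal".

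SAP 4.2.4.2 splits the ITT-i set by oxygen use before treatment. For those on oxygen (partition 1) the question is "Is there a treatment difference in the time to no longer requiring supplemental oxygen", answered by Kaplan-Meier and a stratified Gehan test. For the rest (partition 2) the question is whether oxygen use is prevented, answered by stratified logistic regression. The two p-values are combined by Liptak's method. A further Kaplan-Meier and Gehan analysis uses the total group, with subjects who never need oxygen given an event at time 0.

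On who may enter, Protocol 4.1 gives "Chronic obstructive pulmonary disease (COPD) exacerbation" as an example of an eligible illness, Protocol 8 names "home oxygen therapy" among the therapies to be recorded, and Protocol 4.2 has no exclusion for long-term oxygen.

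**The concern.** A patient who used oxygen at home before RSV, and who goes back to the usual flow, has recovered as far as oxygen can show. Under Table 1 that recovery is not an event. If the oxygen record stays open, the patient falls in partition 1, is censored at about Day 28, and is credited with oxygen for the whole study. The treatment cannot change that outcome.

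The rest of the plan does allow for prior oxygen:

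- The exploratory amount (SAP 4.2) is "Supplemental oxygen above pre-RSV disease level (regardless of method used) from study treatment initiation to Day 7".
- Clinical stability (SAP 4.2) is worded relative to the baseline oxygen requirement.
- Time to SpO2 of at least 93% on room air (Table 1) leaves out prior oxygen users.
- For feeding, Table 1 states its assumption about pre-RSV status openly. For oxygen it gives neither an assumption nor a reference level.

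Duration of supplemental oxygen is a named item of the secondary objectives (SAP 1.1), so what is at stake is the sensitivity of a declared secondary comparison.

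**Working it through.** **1. Is there a figure in the plan to reproduce?** Not for oxygen. The only Part 2 sample-size figures concern viral load AUC (SAP 1.4): about 90% power at an effect size of 0.77 and about 80% at 0.67. With 30 per arm, both active arms at the stated effect and the two planned contrasts, recomputation gives 90.4% to 91.2% and 80.8% to 82.0%. Those figures stand and do not bear on this point.

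**2. Effect on the Gehan statistic.** Gehan scores every active-placebo pair by which patient came off oxygen first. Let D be the expected net score among patients who can reach the event, and c the share of partition 1 with an open home-oxygen record, equal in expectation across arms by randomisation.

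- Neither patient is a home-oxygen user: probability (1-c)², contribution D.
- Only the active patient is one: probability c(1-c), placebo scored as earlier.
- Only the placebo patient is one: probability c(1-c), active scored as earlier. These two cases cancel, provided nearly all other patients come off oxygen before study end.
- Both are: probability c², tied, contribution 0.

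So the expected score becomes (1-c)² × D. The share c is an assumption:

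- c = 5%: 0.95² = 0.90
- c = 10%: 0.90² = 0.81
- c = 20%: 0.80² = 0.64

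The same algebra applies to the total-group analysis with c as the share of the whole group. For example, 2 such patients among 20 in partition 1 (10%), in an arm of 30, give c = 2/30 and a factor of (28/30)² = 0.87.

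**3. What this could mean for power (illustration only).** Every input is assumed: log-normal time to return to the pre-RSV level, placebo median 96 h, log SD 0.9, active/placebo time ratio 0.5, 27 days of follow-up, two-sided 5%, 20 or 30 per arm in partition 1, 4,000 runs per setting. The test is an unstratified Wilcoxon test, which matches Gehan when the only censoring is at a common study end. Thirty per arm is the extreme in which every subject was on oxygen before treatment.

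| Assumed share | Table 1 rule, 20/arm | Table 1 rule, 30/arm |
|---|---|---|
| 0% | 63% | 80% |
| 5% | 54% | 74% |
| 10% | 46% | 62% |
| 20% | 30% | 44% |

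Counting oxygen above the pre-RSV level, power stays at 63% to 65% with 20 per arm and 79% to 82% with 30 per arm, whatever the share. With no treatment effect, rejection stays at about 4% to 5% under both rules.

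**4. Does another planned analysis fill the gap?** Only in part. The amount above the pre-RSV level is merely listed (SAP 4.2.6.2). The Table 1 derivation of clinical stability uses SpO2, respiratory rate, heart rate and feeding, with no oxygen term. The room-air SpO2 endpoint is free of the problem and is compared between arms, but it answers a different question and leaves the oxygen-duration objective as it is.

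**The case against.** The strongest reply is that this is a deliberate and coherent choice. Protocol 2.1.2 lists need for and duration of oxygen with no pre-RSV qualifier, the SAP follows it, and the ordinal scale also counts any oxygen. Total oxygen burden is a legitimate quantity. That stands: this is a design choice, not a conflict between protocol and SAP. It does not explain why the question in partition 1, which is about recovery, should be answered with an event that some patients reach only by giving up their usual therapy.

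Second, a reader might infer that home-oxygen users can never reach the event. The documents do not show this. It depends on how home oxygen is recorded, which they do not say. A user of intermittent oxygen, or one whose in-hospital record closes at discharge, could have an end date. The point holds for continuous users whose record stays open.

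Third, a reader might infer that any drug effect would be masked, or that a chance imbalance would create a false one. Neither follows. The expected difference shrinks but is not erased, and chance imbalance is already within the test's error rate.

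Fourth, one might compare mean oxygen hours, where near-28-day values weigh heavily. The SAP plans no such test; a rank test is less sensitive to them. One might also extend the point to home CPAP, but the documents mention CPAP only as an example of ventilator support.

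Finally, no scheduled item explicitly collects the pre-RSV oxygen flow. That is a fair practical limit, and the fix provides for it.

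**Conclusion.** The point holds as a loss of sensitivity in a secondary endpoint. Table 1 and SAP 4.2.4.2 define duration, end and partition on all oxygen, while three related endpoints allow for prior use. For continuous home-oxygen users with an open record, the partition 1 and total-group Gehan comparisons are diluted, with the expected pairwise difference multiplied by about 0.90, 0.81 or 0.64 at an assumed 5%, 10% or 20% share of partition 1.

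The size rests wholly on that share, which the documents do not give, and on how home oxygen is recorded. The population makes a share of zero hard to assume: COPD exacerbation is eligible, and the Amendment 2 rationale expects many subjects with COPD or asthma.

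Type I error is intact. The partition 2 test is not touched by these patients, so only one component of the combined p-value is diluted. The primary endpoint and the sample size are unaffected.

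**What to change.** Before unblinding, amend SAP Table 1 and 4.2.4.2:

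- Define the event as the last time supplemental oxygen exceeds the pre-RSV level, and duration as time above that level.
- Assign partitions 1 and 2 by whether the subject was above that level before first dose.
- Where the pre-RSV amount is not available for a patient, use the prior-oxygen flag already needed for the room-air SpO2 endpoint and analyse without pre-RSV oxygen users. The flag should refer to the time before respiratory symptoms began, as in Protocol 2.1.2; the SAP dates it to the current hospitalisation.
- State how home oxygen is recorded, including when a record closes.
- Keep the all-oxygen version as a supportive analysis.

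The cost is modest. Pre-RSV oxygen status is already required by the SpO2 endpoint and the level by the exploratory amount, so the work is SAP wording and some programming to compare recorded amounts with the pre-RSV level. The one real downside is that the main analysis would depart from the protocol's unqualified endpoint label; the SAP should say so and point to the supportive version.

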A secondary endpoint of high interest is the length of hospital stay. The length of hospital stay is in hours and taken from the start of treatment initiation to discharge and to readiness for discharge. The differences of active dose regimens versus placebo treatment will be estimated using the accelerated failure time model using appropriate contrasts; baseline covariates such as stratification factors, absence/presence of other viral or bacterial pathogens, RSV baseline log₁₀ viral load, and time from onset of first symptoms to treatment will be added when of predictive value based on blinded data. Treatment effects versus placebo will be reported as acceleration factors including 95% confidence intervals. Subjects for which no time point could be established (eg, withdrawal of informed consent before reaching the endpoint) will be (right-)censored at the latest time point at which it could be established that the endpoint was not reached. Subjects for whom discharge cannot be considered as a marker of adequate recovery (eg, subjects who die during hospitalization or who are transferred to a care facility with the same level of care as during hospitalization) will be censored at the planned final follow-up visit. No adjustments for multiplicity will be made. Analytical details will be provided in the SAP.

While this clinical endpoint is considered of high interest, the current sample size is determined by considerations on antiviral activity; for length of hospital stay the anticipation is that there will be too much heterogeneity to expect statistically significant separation of active groups versus placebo with the current sample size, even if a numerical trend is anticipated.

The impact of the baseline viral genotype and subtype on the antiviral activity will be explored.

Analysis of the viral sequencing results will be described in the SAP.

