1.2. Trial Design

This is a randomized, double-blind, placebo-controlled, parallel-grouped, multicenter, dose-finding study of ALS-008176.

A target of approximately 90 subjects, ≥ 50 years of age who are hospitalized with RSV, will be randomly assigned in this study with 30 subjects planned per treatment regimen.

Subjects will be randomized in a 1:1:1 ratio to Regimen A, B, or C:

- Regimen A (placebo): a single LD (Dose 1) followed by 9 MDs (Doses 2 to 10) of matching placebo, administered twice daily.

- Regimen B (low-dose ALS-008176): a single 750 mg LD (Dose 1) followed by nine 250 mg MDs (Doses 2 to 10) of ALS-008176, administered twice daily.
- Regimen C (high-dose ALS-008176): a single 1,000 mg LD (Dose 1) followed by nine 500 mg MDs (Doses 2 to 10) of ALS-008176, administered twice daily.

The randomization will be balanced by using randomly permuted blocks and will be stratified by region (Japan versus non-Japan) and age (≥ 50 to < 65 years and ≥ 65 years).

The study will be conducted in 3 phases: a screening phase, a treatment phase from Day 1 to Day 5/6 (depending on the timing of the LD), and a follow-up phase for a total of 28 days post randomization. In the follow-up phase, subjects will have assessments completed at Day 7, Day 10, Day 14, and Day 28. Depending on discharge date, assessments will be completed either while hospitalized or during outpatient visits. For hospitalized subjects additional assessments are done as per the Time and Events Schedule. The duration of the subject's participation will be approximately 28 days, screening period not included.

Screening for eligible subjects will be performed as soon as possible following admission to the emergency room or hospitalization, such that subjects are randomized within 5 days of RSV symptom onset. Men or women ≥ 50 years of age diagnosed with RSV infection based on a polymerase chain reaction (PCR)-based diagnostic assay (with or without co-infection with another respiratory pathogen) who have been (or will be) admitted to the hospital and who have signed informed consent will be enrolled.

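### Time to end of oxygen, ventilation, feeding or hydration support never counts a death on support as failure to come off it, so 1 minus Kaplan-Meier overstates the proportion off support alive

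*SAP*

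**What the plan says.** SAP 4.2.4.1, Table 1, covers three oxygen parameters (overall, invasive, non-invasive) and two others (feeding, hydration). For all five:

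- Event: "The event is defined as the last end date and time of the measured parameter".
- No end date: "If this date is missing, the end date is considered to be after study completion or withdrawal".
- Death: "In case of death prior to the last end date and time of the measured parameter, the time of death will be taken". The subject is censored then, with noon substituted when the clock time is unknown.

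For subjects on oxygen before treatment, SAP 4.2.4.2 states: "This analysis will be performed primarily with a Kaplan-Meier analysis and a stratified Gehan test". The resulting p-value is combined by Liptak's method with the logistic test from subjects who were not on oxygen. The oxygen analysis is repeated by method of administration. It is also run on the pooled group, where subjects who never need oxygen have their event at time 0. For the other supports: "The analysis for the need and duration of supplemental feeding and supplemental hydration will be done in similar fashion". No competing-risk method is given for these variables.

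Follow-up is fixed: "a follow-up phase for a total of 28 days post randomization". For length of hospital stay only, Protocol 11.3 says that discharge does not mark adequate recovery in a subject who dies in hospital, and that such a subject "will be censored at the planned final follow-up visit". The protocol has no death rule for oxygen, ventilation, feeding or hydration.

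**The concern.** The endpoint is meant to show how soon subjects no longer need support. A subject who dies on support never reaches that state, but Table 1 has no category for this outcome:

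- If the end date is left blank, the end is deemed to fall after the study. Death comes first, and the subject is censored at death. Kaplan-Meier then treats the subject as someone who could still have come off support later.
- If the end time is entered as the time of death, or just before it, death is not earlier than the end time. Read literally, the subject has the event.

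Two subjects with the same outcome can thus receive opposite codes because of how one field was completed, and neither is recorded as a failure. Duration of supplemental oxygen is a named secondary objective. Need for and duration of oxygen is also one of the secondary endpoints repeated in the PP and ITT sets (SAP 2.3).

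**Working it through.** The plan gives no event count, power or expected proportion for these endpoints, so there is no figure to reproduce. The size of the effect has to be illustrated under assumptions.

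**1. Mortality.** Protocol 1.2 cites 60-day mortality as high as 13.8% in adults hospitalized with RSV. At a constant hazard, 28-day mortality is 1 − (1 − 0.138)^(28/60) = 6.7%. This serves as a ceiling, with 3% as a lower value.

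**2. Worked example.** Take 20 subjects on support. Seventeen come off on Days 2, 3, 4, 4, 5, 6, 7, 8, 9, 10, 11, 12, 14, 16, 18, 21 and 24. Three die on support, on Days 2.5, 4.5 and 5.5.

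| Coding of the 3 deaths | Median (days) | Off support by Day 14 | By Day 28 |
|---|---|---|---|
| Event | 7 | 16/20 = 80% | 20/20 = 100% |
| Censored at death | 9 | 75.5% | 100% |
| Non-event, held to Day 28 | 10 | 13/20 = 65% | 17/20 = 85% |

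For the censored row at Day 14, the Kaplan-Meier product is 19/20 × 17/18 × 15/17 × 13/14 × 4/12 = 0.245, so 1 − KM = 75.5%. The true share alive and off support at Day 28 is 85%.

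**3. Simulation at trial scale.** Assumptions: 20 subjects per arm on oxygen (of 30 planned), oxygen duration lognormal with median 5 days and log-SD 0.9, deaths uniform over Days 1 to 28, 3,000 arms per setting. The missing fact is how many deaths occur on oxygen, so two bounds are shown. In the upper bound every death occurs on oxygen. In the lower bound death is independent of oxygen duration; most deaths then follow weaning, and about 1.5% of subjects die on oxygen at 6.7% mortality.

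| 28-day mortality | Bound | Off oxygen alive | 1 − KM, censored | 1 − KM, event |
|---|---|---|---|---|
| 6.7% | all on oxygen | 90.7% | 94.5% (+3.8) | 97.4% (+6.7) |
| 6.7% | independent | 95.9% | 97.2% (+1.3) | 97.4% (+1.5) |
| 3% | all on oxygen | 94.4% | 96.2% (+1.8) | 97.3% (+2.9) |
| 3% | independent | not tabulated | about +0.6 | about +0.7 |

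Repeat runs agree to 0.1 or 0.2 points. In the first row the standard error of the true proportion is 6.5 points, so +3.8 is 0.58 SE and +6.7 is about 1 SE.

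**4. Closed form, as a check on direction.** With a constant recovery hazard λ and a constant hazard μ of death on support:

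- 1 − KM, deaths censored: 1 − exp(−28λ)
- 1 − KM, deaths as events: 1 − exp(−28(λ + μ))
- alive and off support: λ/(λ + μ) × [1 − exp(−28(λ + μ))]

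For a 7-day median, λ = ln 2/7, so 1 − exp(−28λ) = 1 − 2^(−4) = 93.8%. If 13.8% die on support by Day 28 (the 60-day ceiling used as an extreme), the three values are 93.8%, 96.1% and 82.3%. If 3.3% die on support, they are 93.8%, 94.3% and 91.0%.

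**5. Between-arm test.** Gehan test, 20 versus 20, identical recovery hazards (7-day median), 3,000 runs. Positive Z favours the active arm, which has more deaths on support.

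| Deaths on support, active vs placebo | Event | Censored at death | Held to Day 28 |
|---|---|---|---|
| 13.8% vs 3.3% | mean Z +0.32 | about 0 | −0.30 |
| 20% vs 5% | +0.47 | about 0 | −0.43 |

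In the first row, P(Z > 1.96) is 5.4% with event coding and 2.6% with censoring at death.

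**The case against.** **Death is not written as an event.** Table 1 names death once and assigns it to censoring. The event route needs an end time entered at or before death, and the eCRF and its completion guidelines are not in the documents. A reader might infer that the SAP scores deaths as recovery outright; the text does not go that far. What stands is that the wording permits this coding and does not settle the tie.

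**The treatment comparison.** A reader might infer that the Gehan test and the Liptak combination reward the arm with more early deaths. Under the written rule, with death unrelated to recovery time, the test is unmoved (mean Z about 0). Bias needs event coding, or informative censoring in which those who die would have been slow to wean. That is plausible, but the documents do not quantify it.

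**Size.** The 13.8% is a ceiling from another population over 60 days. This trial excludes subjects not expected to survive 48 hours, immunocompromised subjects, those with eGFR below 60 and those on ECMO. If many deaths follow weaning, the overstatement is 1 to 2 points or less. Hence the range.

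**No contradiction on oxygen.** The Protocol 11.3 rule covers hospital stay only, so Table 1 does not conflict with it on support. A reader might also assume that the SAP follows that rule for hospital stay. It does not: the length-of-stay rows of Table 1 censor at death, and that is a direct protocol-SAP conflict.

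**Death is reported elsewhere**, as the worst ordinal category and as all-cause mortality. That is true, but it does not correct the support curves.

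**Conclusion.** The point holds for the estimated proportions and medians. Under either coding a death on support is not counted as failure to come off it, and 1 − KM is too high. At 6.7% mortality the overstatement at Day 28 is about 1.3 to 3.8 points with deaths censored and 1.5 to 6.7 with deaths as events. At 3% it is about 0.6 to 1.8 and 0.7 to 3 points. These figures rest on the assumed oxygen-duration distribution, and the upper ends assume that every death occurs on support.

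For the treatment comparison the claim is conditional: bias towards the arm with more deaths arises only with event coding or informative censoring. These are secondary endpoints, and the primary viral-load AUC is not touched. The change should be made before unblinding, so that the coding of deaths is not chosen after the fact.

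**What to change.** - In SAP Table 1, for every time-to-end parameter (oxygen, invasive and non-invasive ventilation, feeding, hydration), state that a subject who dies while on the support does not have the event and is carried as a non-event to the Day 28 visit. Include a subject whose recorded end time coincides with death. This applies the principle of Protocol 11.3 for hospital stay.
- Report the cumulative incidence of coming off support alive in place of 1 − KM.
- Keep the censor-at-death analysis as a sensitivity analysis.
- Reconcile the length-of-stay and readiness-for-discharge rows of Table 1, which censor at death, with Protocol 11.3, which carries deaths to the final visit.

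The cost is SAP wording and a derivation change, with no new data. The downside is a change of estimand. The result becomes a subdistribution quantity that partly reflects mortality: the Gehan statistic moves against the arm with more deaths (−0.30 in the first simulated case), and the proportions are slightly less favourable when deaths occur. An end time recorded shortly before death would still count as an event. Neither document gives a window for that case, and none is added here.
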